### 8.3 SAFETY AND OTHER ASSESSMENTS

Participants (prescribers) will not undergo any procedures. Prescribers’ patients will be monitored for adverse events through the DSMB review.

DSMB will monitor for adverse events every 6 months. Adverse events will be measured up to 30 days after the alert or notification occurred. The safety outcomes being monitored by the DSMB include bleeding and thromboembolic events (including stroke and venous thromboembolism). These will be identified through diagnostic code searches within the EHR (see appendix A) and will undergo adjudication as described below.

Investigators will report serious adverse events in accordance with IRBMED requirements. The investigator will follow usual clinical practices at UM for reporting to regulatory authorities serious, unexpected events related to standard of care medications and devices.

## 8.4 ADVERSE EVENTS AND SERIOUS ADVERSE EVENTS

### 8.4.1 DEFINITION OF ADVERSE EVENTS (AE)

An adverse event (AE) is any untoward or unfavorable medical occurrence associated with the subject's participation in the research, whether or not considered related to the subject's participation in the research (modified from the definition of adverse events in the 1996 International Conference on Harmonization E-6 Guidelines for Good Clinical Practice) (from OHRP "Guidance on Reviewing and Reporting Unanticipated Problems Involving Risks to Subjects or Others and Adverse Events (1/15/07)" <http://www.hhs.gov/ohrp/policy/advevntguid.html#Q2>).

### 8.4.2 CLASSIFICATION OF AN ADVERSE EVENT

AEs will be graded for severity and relationship to the intervention by the investigator according to the guidelines to be specified below.

#### 8.4.2.1 SEVERITY OF EVENT

The following guidelines will be used to grade severity of AEs:

Bleeding related events, as defined by the International Society on Thrombosis and Haemostasis (ISTH):

- Major,
- clinically relevant, non major
- minor

Thrombotic (stroke and venous thromboembolism):

- There will be no severity grading of thrombotic events.

Any bleeding or new thrombotic event that occurs within 30 days of a study alert or notification will be included as an adverse event.

Serious adverse events include any death or life threatening outcome. This includes ISTH major bleeding event and any new thrombotic event that occurs within 30 days of a study alert or notification.

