## 2 INTRODUCTION

### 2.1 BACKGROUND AND STUDY RATIONALE

[figure not shown]
**Direct Oral Anticoagulant (DOAC) use is rapidly expanding for six million Americans with common thrombotic conditions.** Atrial fibrillation (AF) and venous thromboembolism (VTE) are the leading indications for chronic anticoagulation therapy. Since 2010, four DOAC medications (apixaban, dabigatran, edoxaban, and rivaroxaban) have rapidly overtaken warfarin as first-line therapy for AF and VTE. DOAC therapy is critical to prevent life-threatening stroke and thromboembolic complications.

**Unsafe DOAC prescribing is common and dangerous.** While initially heralded as easier to prescribe than warfarin, in real-world settings 10-20% of DOAC prescriptions do not follow the Federal Drug Administration (FDA) evidence-based package label instructions. The most common reasons for unsafe DOAC use include inappropriate

dosing based on renal or liver function, overlooked drug-drug interactions, and dosing based on the wrong indication (e.g., using AF dosing for VTE). These prescribing errors occur both at the time of initial prescription and in the months to years of follow up (**Figure 1**). Data from both large national registries and our local studies confirm a higher rate of bleeding, hospitalization, and death for patients with unsafe DOAC use as compared to evidence-based prescribing. Despite these common prescribing errors, most health systems only provide alerts for potential drug-drug interactions, not for other (more common) causes of inappropriate DOAC prescribing.

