Clinical adverse events assessed will include major and clinically-relevant non-major bleeding (CRNMB) events, as defined by the International Society on Thrombosis and Haemostasis (ISTH), new or recurrent VTE events, and stroke or systemic arterial embolic events objectively identified by imaging and identified as a new event by their primary clinical provider. Transient Ischemic Attacks (TIAs) that do not result in findings on imaging (such as CT or MRI) will not be included. Each of these events will be captured using health informatics tools (described below) and adjudicated every six months. Adjudication will occur at least one month prior to six month DSMB meetings to allow for the DSMB to review findings in advance of the meeting. We will use Michigan Medicine-developed health informatics tools to create a report that identifies all patients whose prescribers have received an alert or notification and any adverse event diagnosis codes within 30 days thereafter. These cases will then be reviewed by the adjudicators to determine if an adverse event occurred and if it was associated with medication management, as defined in Section 8.4.2.2. The adjudicators will have access to all laboratory and medication data as well as clinical notes, but will be blinded to group allocation. The report, created by Michigan Medicine health informatics research team, will undergo a validation process for accuracy by the study team leads, including a cardiovascular physician and pharmacist.

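### Any death counts as a serious adverse event, but case finding targets bleeding and thromboembolic events and no source or time window for deaths is given

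*Combined protocol and SAP*

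**What the plan says.** **Definition.** Section 8.4.2.1 first sets the adverse event rule: "Any bleeding or new thrombotic event that occurs within 30 days of a study alert or notification will be included as an adverse event". It then says: "Serious adverse events include any death or life threatening outcome". That sentence restricts death neither by cause nor by time. The section adds that major bleeds and new thrombotic events within 30 days are serious.

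**What is monitored.** The DSMB outcomes in 8.3 are bleeding and thromboembolic events. The adjudicated clinical events in 8.1 and 9.3.4 are major and clinically relevant non-major bleeding, venous thromboembolism, and stroke or systemic arterial embolism. Neither list names death.

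**How cases are found.** Section 8.3 says: "These will be identified through diagnostic code searches within the EHR (see appendix A) and will undergo adjudication as described below". Section 9.3.4 describes a report that "identifies all patients whose prescribers have received an alert or notification and any adverse event diagnosis codes within 30 days thereafter", and continues: "These cases will then be reviewed by the adjudicators to determine if an adverse event occurred". Section 8.1 adds two informatics tools that allow free-text searches of the record, with bleeding and stroke as the example terms. Appendix A, which is to hold the code list, is a placeholder.

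**How cases are used.** Section 9.3.6 tabulates serious and non-serious events overall and by randomization group, and lets the trial be halted or modified if adverse events differ between arms at p<0.01. Section 8.4.2.2 uses the timing of adverse events to judge whether the 15-day dashboard embargo may have contributed to harm.

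**The concern.** The protocol's own definition includes an outcome for which it states no means of detection. The rationale in 2.1 makes that outcome relevant, because it cites data that "confirm a higher rate of bleeding, hospitalization, and death for patients with unsafe DOAC use as compared to evidence-based prescribing". The trial also holds back an existing safety pathway, the pharmacist dashboard, for 15 days.

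If deaths are not looked for, the by-arm table of serious events may omit the most serious of them. The p<0.01 comparison cannot use them, and the embargo check, which begins from identified adverse events, cannot examine them. The primary and secondary prescription-change outcomes are not affected.

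**Working it through.** The plan gives no figure for deaths, so there is none to reproduce. The check traces the text and then gauges the scale.

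**Tracing a death through the plan**

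1. *Death in hospital after a coded bleed or an imaged stroke.* The code search flags the patient, adjudicators see the case, and the death comes to light with the index event. The plan works here.
2. *Fatal stroke or systemic embolism before work-up, for example at home.* Section 9.3.4 admits only "stroke or systemic arterial embolic events objectively identified by imaging and identified as a new event by their primary clinical provider". Without imaging the event cannot qualify, and there may be no diagnosis code to flag the patient.
3. *Death from another cause.* It is serious under 8.4.2.1 as worded, but no bleeding or thrombotic code or term is expected.

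In cases 2 and 3 no passage sends the patient to the adjudicators. The later steps (the relatedness grading, DSMB review and embargo check in 8.4.2.2, and the table and comparison in 9.3.6) all start from identified events. An unflagged patient who remains in the denominator is by default a patient without an event. That last step is an inference; no section says it.

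**Scale**

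Inputs from 9.1: 300 prescribers with an average of 2 patients (3 in the less conservative case), and planned adverse event rates of 1% versus 0.5%.

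- Patients: 300 × 2 = 600, or 300 per arm.
- Expected flagged events: 300 × 0.01 + 300 × 0.005 = 3.0 + 1.5 = 4.5.
- With 3 patients each: 900 patients, 450 × 0.01 + 450 × 0.005 = 4.5 + 2.25 = 6.75.

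Assumed inputs, since the documents give no mortality: 30-day all-cause mortality q from 0.1% to 1%, and share s of deaths with no bleeding or thrombotic flag from 50% to 100%.

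- Missed deaths = N × q × s.
- Chance of missing at least one = 1 − (1 − q × s)^N.

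| q | s | Missed in 600 | Chance of at least one in 600 | Missed in 900 |
|---|---|---|---|---|
| 0.1% | 50% | 0.3 | 26% | 0.45 |
| 0.5% | 75% | 2.25 | 90% | 3.38 |
| 1% | 100% | 6.0 | over 99% | 9.0 |

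Missed deaths equal the 4.5 expected events when q × s = 4.5 / 600 = 0.75%. They are therefore as numerous as the flagged events only near the top of the assumed range. At the bottom they are 0.3 / 4.5, or about 7% of them.

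**Bleeding lists**

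Section 8.4.2.1 counts bleeding of every grade and includes a minor grade. Sections 8.1 and 9.3.4 list only major and clinically relevant non-major bleeding. These do not agree.

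**The case against.** The strongest reply is that the sentence on death in 8.4.2.1 only grades events already defined as bleeding or thrombosis. The section opens as a guide to severity, and the sentence follows the 30-day rule for those events. On that reading serious events are a subset of the adverse events, and case finding matches. The wording allows this reading, but two things count against relying on it. Section 8.4.3 expects serious events judged unrelated to the intervention to be reported to the IRB in aggregate, which fits a broader definition, although it does not settle the matter because a bleed may also be unrelated. And even on the narrow reading, a fatal arterial event before imaging still has no route.

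A reader might also infer more than the documents support:

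- *That patients are found only by diagnosis codes.* Section 8.1 adds text searches, and its terms are examples.
- *That such deaths are never captured.* Appendix A is not filled in, so death codes are neither included nor excluded. Serious-event reporting under IRB requirements (8.3), reporting of unanticipated problems (8.5.2), review of randomly selected cases (8.4.2.2) and the DSMB's general remit (10.1.6) could each bring a death to light. None is a systematic search for deaths.
- *That one arm will look safer.* The same search applies to all arms and adjudicators are blinded, so a distortion requires missed deaths to differ by arm, which nothing in the documents shows. As a competing event alone, 1% mortality would lower a 1% event rate only to 0.01 × 0.99 = 0.99%.
- *That systemic embolism is also missing from 8.4.2.1.* That section covers every new thrombotic event, so the mismatch is weak.

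**Conclusion.** The point stands in this form: the plan makes any death serious, directs case finding at bleeding and thromboembolic events, and names no source or window for deaths. A death without such a flag has no stated route into adjudication, the by-arm safety table, the p<0.01 comparison or the embargo check, and would by default be counted as no event.

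The size is not known. About 0.3 to 6 missed deaths in 600 patients, against 4.5 expected events, rests entirely on the assumed mortality and unflagged share. With so few expected events, one or two missed deaths could alter the safety picture. The direction of any between-arm bias is unknown. The text shows a gap in the stated plan for safety capture; it does not show that deaths will in fact be lost.

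**What to change.** - In 9.3.4, add all-cause death within 30 days of the alert or notification, taken from EHR vital status and date of death, as a trigger in the existing report.
- In 8.3, add death to the DSMB outcomes.
- Send each death to the existing blinded adjudicators, so that it also enters the embargo check in 8.4.2.2.
- In 9.3.6, tabulate deaths by arm. A composite of death, major bleeding and thrombosis is optional.
- Use one bleeding list in 8.1, 8.4.2.1 and 9.3.4, and say whether minor bleeds are collected.

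If the sponsor intends the narrow reading, the sentence in 8.4.2.1 should be reworded to match what is collected. That removes the inconsistency but leaves other deaths unseen.

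The cost is an added field in a report already planned and a few extra cases to adjudicate. Some deaths will be unrelated to DOACs, and deaths outside the health system may be recorded late.

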#### 8.4.2.2 RELATIONSHIP TO STUDY INTERVENTION

Our protocol is intended to increase adherence to evidence based prescribing. Adverse outcomes will be assessed in relation to the degree to which prescribers adhered to evidence-based prescribing.

Use of evidence based prescribing (Appendix B) will be evaluated by blinded adjudicators (one pharmacist, one prescribing clinician) at the time of any adverse event as well as randomly selected cases. The following categories will be used:

Initially, each adverse event will be examined with regard to medication management. Cases will be classified into one of the following 5 categories:

1. **Definitely appropriate medication management** – There is clear evidence to suggest that prescribers considered the appropriate clinical factors and prescribed medication in accord with evidence based prescribing. (Example: Rivaroxaban dose changed from 15->20mg daily in a patient with atrial fibrillation, creatinine clearance 75 ml/min, and no drug drug interactions)
2. **Probably appropriate medication management** – There is some evidence to suggest that prescribers considered the appropriate clinical factors and prescribed medication in accord to evidence based prescribing. (Example: Rivaroxaban dose changed from 15->20mg daily in a patient with atrial fibrillation, creatinine clearance of 51ml/min [previously 48 ml/min], and no drug-drug interactions)
3. **Probably inappropriate medication management** – There is some evidence to suggest that the prescriber may have deviated from evidence based prescribing. (Example: Rivaroxaban dose changed from 15->20mg daily in a patient with atrial fibrillation, creatinine clearance of 48 ml/min [previously 55 ml/min], and no drug-drug interactions)
4. **Definitely inappropriate medication management** – There is clear evidence to suggest that the prescriber deviated from evidence based prescribing. (Example: Rivaroxaban dose changed from 15->20mg daily in a patient with atrial fibrillation, creatinine clearance of 35 ml/min, and no drug-drug interactions)
5. **Unable to assess appropriateness of medication management:** Due to lack of information in the medical record, it is not possible to assess the appropriateness of the medication management.

Adverse events that are classified in the Medication Management categories 3, 4 or 5 above will then be reviewed with regard to whether the adverse event is related to the prescription. The following 5 categories will be used:

- A. **Definitely not related**—The clinical event, despite occurring in a plausible time relationship to study intervention administration, can be explained by concurrent disease or mechanism, or other other drugs or chemicals, or is a non-preventable medication adverse event.
- B. **Probably not related** —The clinical event, despite occurring in a plausible time relationship to study intervention administration, is **more likely than not** explained by concurrent disease or mechanism, or other other drugs or chemicals, or is a non-preventable medication adverse event.

- C. **Probably related** – It is **more likely than not** that a causal relationship exists between the adverse event and the prescription. However, other factors may have contributed to the event (e.g., the participant's clinical condition, other concomitant events).
- D. **Definitely related** – There is no significant evidence that suggests other drugs or chemicals or underlying disease provides plausible explanations (e.g., the participant's clinical condition, other concomitant treatments).
- E. **Unable to assess relatedness of medication management**: Due to lack of information in the medical record, it is not possible to assess the relationship between the adverse event and the prescription.

Adverse events that are classified into categories of C, D, or E (as well as categories 3, 4, and 5) will be reviewed by the DSMB. This includes all cases in which the medication management was more likely than not inappropriate medication management, and adverse events which are more likely than not related to the medication. It also includes all cases where the medication management and the relationship of the medication to the adverse event is unknown.

All adverse events (serious and non-serious) will further be assessed based on the time from medication error until the adverse event occurred. This will be done to determine if the 15 day embargo on the existing dashboard may have contributed to patient harm. Specifically, we will look to see if medication alerts or notifications were not addressed through the study interventions that may have been addressed via the dashboard if no embargo were in place.

---

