## 2.2 RISK/BENEFIT ASSESSMENT

### 2.2.1 KNOWN POTENTIAL RISKS

There are minimal risks to the subjects (prescribers).

- Confidentiality
- Risk to reputation if “errors” are revealed to Michigan Medicine administrators
- Alert fatigue
- The alert and notifications may recommend a medication change that is harmful for the patient

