#### 8.4.3 ADVERSE EVENT REPORTING

All reporting comply with Michigan Medicine IRB guidelines

(<https://az.research.umich.edu/medschool/guidance/adverse-event-reporting>).

Any serious adverse event that are adjudicated as being definitely or possibly related to the study intervention will be reported to the IRB within 7 calendar days of the study team becoming aware of the event.

All non-serious adverse events that are adjudicated as being definitely or possibly related to the study intervention will be reported to the IRB in aggregate at least annually.

All serious adverse events that are adjudicated as being definitely or possibly unrelated to the study intervention will be reported to the IRB in aggregate at least annually.

All non-serious adverse events that are adjudicated as being definitely or possibly unrelated to the study intervention will be collected for analysis but not reported to the IRB.

All adverse events in which the adjudication team is unable to assess the relatedness to the study intervention will be reported to the IRB in aggregate at least annually.

---

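### Adverse events after appropriate prescribing get no relatedness grade, so no Section 8.4.3 IRB reporting rule applies to them; the grading and reporting scales also differ

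*Combined protocol and SAP*

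**What the plan says.** Section 8.4.2 commits to grading adverse events for severity and for relationship to the intervention. Section 8.4.2.2 then sets up two stages. Blinded adjudicators first place each event in one of five medication-management categories: 1 and 2 are definitely or probably appropriate, 3 and 4 probably or definitely inappropriate, and 5 not assessable. The second stage is restricted: "Adverse events that are classified in the Medication Management categories 3, 4 or 5 above will then be reviewed with regard to" a relatedness grade from A to E. The question asked there is "whether the adverse event is related to the prescription", and grade C is defined by it being more likely than not "that a causal relationship exists between the adverse event and the prescription". DSMB case review is tied to grades C, D or E together with categories 3, 4 or 5.

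Section 8.4.3 sets the IRB reporting rules. For serious events the trigger is "adjudicated as being definitely or possibly related to the study intervention will be reported to the IRB within 7 calendar days". Three further rules use the same *definitely or possibly* wording, for related non-serious events and for unrelated serious and non-serious events. A fifth covers events whose relatedness the adjudicators could not assess.

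Among the known risks, Section 2.2.1 lists: "The alert and notifications may recommend a medication change that is harmful for the patient".

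**The concern.** The alert logic is built on approved labelling and trusted sources (risk mitigation text in Section 2). A prescriber who follows a sound recommendation will therefore normally be graded as prescribing appropriately. If the patient then has a major bleed or a clot within 30 days, Section 8.4.2.1 makes that a serious adverse event. Yet nobody is asked whether it was related to the study intervention, because the good prescribing grade ends the process. The IRB rules all presuppose that this question has been put.

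At stake is case-level safety oversight: whether a serious event plausibly linked to an alert or notification has a defined path to the 7-day report and to DSMB case review. The primary outcome analysis is not affected.

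**Working it through.** The plan gives no figure to reproduce on this point. The check traces the categories through the rules, followed by a short calculation on the statistical backstop.

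**Step 1. Trace each outcome of adjudication through Sections 8.4.2.2 and 8.4.3.**

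| Management category | Relatedness grade | Matching rule in 8.4.3 | DSMB case review |
|---|---|---|---|
| 1 or 2 | none given | none | no |
| 3, 4 or 5 | A, definitely not | definitely unrelated | no, if the two conditions are read jointly |
| 3, 4 or 5 | B, probably not | no literal match (rule says possibly unrelated) | as for A |
| 3, 4 or 5 | C, probably | no literal match (rule says possibly related) | yes |
| 3, 4 or 5 | D, definitely | definitely related | yes |
| 3, 4 or 5 | E, cannot assess | unable to assess | yes |

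So 2 of 5 management categories reach no reporting rule, and 2 of 5 relatedness grades have no literal counterpart. The rule for events that cannot be assessed does not rescue categories 1 and 2, since it presupposes an attempt. These categories stay outside DSMB case review on any reading of that sentence, because they carry neither a grade C to E nor a category 3 to 5.

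**Step 2. Compare the object of the judgement.** Section 8.4.2 promises a grade against the intervention, the A to E question is put against the prescription, and Section 8.4.3 acts on relatedness to the study intervention. Grades A and B also absorb non-preventable adverse events of the drug. Sending categories 1 and 2 to the present scale would therefore not be enough; the question itself has to change.

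**Step 3. List what else covers a category 1 or 2 event.**

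- Capture as an adverse event within 30 days (8.4.2.1) and a management grade (8.4.2.2).
- The timing review of all events (8.4.2.2). It asks whether the 15-day dashboard embargo left an error uncorrected, not whether a followed alert did harm.
- Unanticipated-problem reporting within 24 hours (8.5.2). Section 8.5.1 requires the event to be related or possibly related to participation, and that judgement is missing here.
- Tabulation by arm with a possible halt at p < 0.01 (9.3.6), and adverse events in DSMB reports (10.1.6).

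**Step 4. How sensitive is the p < 0.01 comparison?** Inputs from Section 9.1: event rates of 1% and 0.5%, and 300 prescribers with 2 or 3 patients each. This gives 300 × 2 / 2 = 300 or 300 × 3 / 2 = 450 patients per arm. The 3% and 1% rates are my assumption, for range. Patients are treated as independent.

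Expected events = n(p1 + p2). Chance of crossing = sum over x and y of Bin(x; n, p1) × Bin(y; n, p2), taken where the two-sided p-value is below 0.01. The p-value comes from Fisher's exact test or from z = (|x − y| / n) / √(2p(1 − p) / n), with p = (x + y) / 2n.

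| n per arm | Rates | Expected events | Fisher | Pooled z |
|---|---|---|---|---|
| 300 | 1% v 0.5% | 300 × 0.015 = 4.5 | 0.3% | 0.8% |
| 450 | 1% v 0.5% | 450 × 0.015 = 6.75 | 1.1% | 2.2% |
| 300 | 3% v 1% | 300 × 0.04 = 12 | 11% | 16% |
| 450 | 3% v 1% | 450 × 0.04 = 18 | 25% | 32% |

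There is also a structural limit. Sections 5.4 and 6.1.1 describe the same warning content within each pair of arms, which differ only in the pharmacist link or the routing. Harm from following a recommendation may therefore fall on both arms alike and produce no contrast, whatever the numbers.

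**The case against.** The strongest defence is that this is deliberate triage. Section 8.4.2.2 opens by saying that the intervention aims at adherence to evidence-based prescribing and that events will be assessed against that aim. A bleed under correct dosing is then an accepted hazard of the drug. Several parts of the defence stand.

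- A reader might infer that such events cannot be classified or reported at all. The documents do not support that: the routes in step 3 exist. Sections 8.3 and 8.4.3 also bind reporting to institutional IRB requirements, which are not reproduced and could add a path.
- A reader might infer that every harm from a followed alert escapes review. That does not follow. Adjudicators grade the prescription against guidance, not compliance with the alert. An alert that was wrong for the patient could lead to category 3 or 4 and so to relatedness grading. The gap is confined to events after guideline-concordant prescribing.
- The mismatch between *probably* and *possibly* is probably a slip. An event more likely than not related is at least possibly related, and the five grades line up in order with the reporting terms. The text does not say so, however.
- The section title and grades A and B do mention the study intervention, so the difference in object is an inconsistency within the section rather than a clear choice.

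The triage argument does not answer the main point. Section 8.4.2 promises a relationship grade without exception, and Section 8.4.3 has no rule for an event that was never graded. Of the remaining routes described in the plan, one needs the missing judgement, one asks a different question, and the others rest on aggregate counts.

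**Conclusion.** The point holds at the level of the individual event. After appropriate prescribing there is no relatedness grade, no applicable rule in Section 8.4.3 and no DSMB case review. A serious event plausibly linked to the intervention then has no defined path to the 7-day report. The size is 2 of 5 management categories without a rule and 2 of 5 relatedness grades without a literal match. This rests on reading the restriction to categories 3 to 5 as written, and on the unseen institutional guidance not filling the gap.

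Two larger claims should not be made. A reader might take the 40% to 60% pilot change rates in Section 9.1 to mean that about half of post-alert events go ungraded. Those rates describe prescriptions changed, not how adverse events divide among management categories, so no share can be given. A reader might also conclude that deaths are being missed. Section 8.4.2.1 says "Serious adverse events include any death or life threatening outcome", and Section 8.3 says of the monitored bleeding and thromboembolic outcomes "These will be identified through diagnostic code searches within the EHR". But Section 8.1 adds text searches of the record, the code list is not in the document, and the line on death may only be a seriousness criterion for bleeding and thrombotic events. That is a secondary ambiguity to settle.

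**What to change.** Reconcile Sections 8.4.2, 8.4.2.2 and 8.4.3:

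1. Have the existing adjudicators grade every adverse event, whatever its management category, for relatedness to the study alert or notification. Word the question generically, without reference to routing or the pharmacist link, so that they stay blinded to allocation.
2. Use one object and one scale in both sections, for example by stating that *probably* in 8.4.2.2 is the *possibly* of 8.4.3, on both the related and the unrelated side.
3. State the IRB rule and the DSMB review rule for category 1 and 2 events explicitly.
4. State whether a death within 30 days that carries no bleeding or thrombosis code is captured.

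The cost is a wording amendment, one added question per case already under review, and some more IRB reports. At the event rates in Section 9.1 the caseload is small: 4.5 to 6.75 expected events per factor.

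### In 8.4.2.2 the test for category A is looser than for B and overlaps C, so serious thrombotic events and non-preventable bleeds can lose 7-day IRB reporting

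*Combined protocol and SAP*

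**What the plan says.** Section 8.4.2.2 adjudicates in two steps. Medication management is graded 1 to 5. Events "classified in the Medication Management categories 3, 4 or 5 above will then be reviewed with regard to whether the adverse event is related"; relatedness here means relation to the prescription and is rated on a scale from A to E.

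- **A, definitely not related:** the event "can be explained by concurrent disease or mechanism, or other other drugs or chemicals, or is a non-preventable medication adverse event"; no probability qualifier is attached.
- **B, probably not related:** on a more-likely-than-not standard, the event is judged "explained by concurrent disease or mechanism, or other other drugs or chemicals, or is a non-preventable medication adverse event"; the list of alternatives is the one used in A.
- **C, probably related:** a causal link to the prescription is more likely than not. The text adds: "However, other factors may have contributed to the event", with the patient's clinical condition as an example.
- **D, definitely related:** "There is no significant evidence that suggests other drugs or chemicals or underlying disease provides plausible explanations".
- **E:** relatedness cannot be assessed.

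On DSMB case review, the same section says that events "classified into categories of C, D, or E (as well as categories 3, 4, and 5) will be reviewed by the DSMB".

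Section 8.4.2.1 defines serious events: "This includes ISTH major bleeding event and any new thrombotic event that occurs within 30 days of a study alert or notification". Section 8.4.3 gives the 7-calendar-day IRB report only to serious events adjudicated definitely or possibly related to the study intervention. Serious events judged unrelated, and events that cannot be assessed, go to the IRB in aggregate at least annually.

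Section 2.1 describes the treated population: "Atrial fibrillation (AF) and venous thromboembolism (VTE) are the leading indications for chronic anticoagulation therapy".

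**The concern.** The scale reads as if written for drug toxicity, where underlying disease competes with the drug as an explanation. Here many of the monitored harms are thrombotic events that the DOAC is prescribed to prevent. For those, the underlying disease is the reason for treatment and will almost always be an available explanation. An adjudicator can therefore judge a prescription inappropriate because it gave too little anticoagulant, then follow the wording to the label *definitely not related* for the stroke that followed.

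A and B also admit a drug event judged not preventable. That concerns preventability, not causation. A bleed that the DOAC did cause can satisfy A and C together, and nothing says which prevails.

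What is at stake is prompt reporting. The sample notification in 2.1 recommends a dose reduction, and 2.2.1 lists a harmful recommended change among the known risks. Too little anticoagulation is thus a foreseeable route to harm. The four worked examples for management categories 1 to 4 all describe a dose increase, so none guides adjudicators on an under-dosed case.

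**Working it through.** The plan gives no figure for this point. The check is a comparison of definitions, followed by a trace of each rating through the reporting rules.

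**Step 1. Order of the tests.**

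| Category | Strength of label | What another cause must do |
|---|---|---|
| A | definite | be able to explain the event |
| B | probable | explain it more likely than not |
| C | probable | may contribute, but the prescription is more likely than not causal |
| D | definite | not be supported as a plausible explanation |

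Anything that meets B on disease grounds also meets A, so A is the wider category despite its stronger label. An event can also meet A (disease can explain it) and C (the prescription more likely caused it, with disease contributing).

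**Step 2. Stroke in AF, or recurrent VTE, after management rated 3 or 4.** The indication can explain the event, so A is open. The indication is a plausible explanation, so D is effectively closed. C remains open because it tolerates a contributing clinical condition. The choice between A and C is left to the adjudicators.

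**Step 3. Routing.** Three management categories (3, 4, 5) times five relatedness categories give 15 combinations. Every new thrombotic event within 30 days is serious.

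| Rule | Combinations included | Not included |
|---|---|---|
| 7-day IRB report (8.4.3), taking *possibly* to mean *probably* | C, D: 3 × 2 = 6 | A, B, E: 3 × 3 = 9 |
| DSMB case review, *as well as* read as AND | C, D, E: 3 × 3 = 9 | A, B: 3 × 2 = 6 |
| DSMB case review, *as well as* read as OR | 15 | 0 |

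The sentence that follows the DSMB rule says review covers all cases in which management was more likely than not inappropriate. Taken alone, it includes all 2 × 5 = 10 combinations with category 3 or 4, whatever the A–E rating.

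A case rated 3-A or 4-A therefore misses the 7-day report under either reading of the DSMB rule. It misses DSMB case review only under AND.

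**Step 4. Size.** Section 9.1 assumes 300 prescribers with 2 patients each, or 600 patients per comparison and 300 per arm, with adverse event rates of 1% and 0.5%:

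300 × 0.01 + 300 × 0.005 = 3 + 1.5 = 4.5 events.

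These are bleeding and thrombotic events together. Only those that are serious, follow management rated 3 to 5, and are then rated A or B are affected. The documents give none of these fractions.

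**The case against.** **Category A is permitted, not forced.** C accepts that the patient's condition contributed, and two blinded clinicians adjudicate. If they think under-dosing caused a stroke, they may choose C. Being unable to reach D costs little, because C and D are routed alike to the DSMB, and alike to the IRB if *probably* and *possibly* are equated. This stands. The defect is that the wording supports two opposite answers with different reporting consequences.

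**Loss of DSMB case review is not established.** A reader might infer that A and B cases never reach the DSMB. That needs the AND reading, which sits badly with the explanatory sentence. AND has some support: if every category 3 to 5 case goes to the DSMB anyway, the A–E rating has no effect on DSMB routing. The rule is ambiguous and no more can be claimed.

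**The events stay visible elsewhere.** A reader might also infer that the DSMB will see almost only bleeds. The documents do not support this. The loose wording affects bleeds as well, through the preventability clause. The DSMB monitors bleeding and thromboembolic events every 6 months (8.3), its reports include adverse events (10.1.6), and 9.3.6 tabulates serious and non-serious events by arm. All adverse events also get the embargo timing review (8.4.2.2). None of these states a relatedness filter.

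**The 7-day consequence involves an inference.** Section 8.4.2.2 says *probably* and rates relation to the prescription; 8.4.3 says *possibly* and refers to the study intervention. No mapping is given. An A rating nevertheless falls on the unrelated side under any natural mapping, and the mismatch itself needs correcting.

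**Conclusion.** The concern holds as a defect in the relatedness definitions. A is looser than B, A overlaps C, and A and B mix causation with preventability. In consequence, a serious thrombotic event after inappropriate prescribing, or a DOAC-caused bleed judged non-preventable, may be labelled unrelated and reported to the IRB only in aggregate. This rests on reading the categories literally and on equating the labels of 8.4.2.2 with those of 8.4.3. Loss of DSMB case review is possible but not shown.

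The number of events affected cannot be derived; it is at most a small subset of about 4.5 per comparison under the 9.1 assumptions. One might apply an assumed thrombotic share of 25% to 50% (4.5 × 0.25 = 1.1; 4.5 × 0.50 = 2.25) and conclude that one or two serious events are screened out. That would skip the restriction to management categories 3 to 5 and treat an A or B rating as automatic.

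Nor do the documents support arguing that under-dosing must at least double risk before C can apply. The protocol does not make a population attributable fraction the rule for judging a single case.

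With so few events, by-arm counts carry little signal and individual adjudication matters more. The point should be corrected, but it does not undermine the trial's safety oversight as a whole.

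**What to change.** Amend 8.4.2.2, 8.4.3 and the adjudication form:

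1. Make A stricter than B, for example by requiring that another cause fully explains the event and that a contribution from the prescription is excluded.
2. State that, for thrombotic events, the DOAC's indication alone does not qualify as concurrent or underlying disease in A, B or D. Keep the more-likely-than-not threshold for C the same as for bleeds, so that the two kinds of harm are judged alike.
3. Remove the non-preventable clause from A and B. Record preventability as a separate item with no effect on DSMB or IRB routing.
4. State that every event in management category 3, 4 or 5 goes to DSMB case review whatever its A–E rating. This agrees with the existing explanatory sentence.
5. Use one set of labels (*probably* or *possibly*) and one referent (the prescription or the study intervention) in both sections.

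The cost is an amendment to text and form. A few more cases will go to the DSMB and the IRB. No treatment rule changes.
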